4.6. Lost to Follow-Up

A patient will be considered lost to follow-up if he/she repeatedly fails to return for scheduled visits and is unable to be contacted by the study site.

The following actions must be taken if a patient fails to return for any required study visit:

- The site must attempt to contact the patient and reschedule the missed visit as soon as possible. If possible, the site should attempt to reschedule the missed visit within any allowed visit or treatment window;
 - The site should advise the patient that it is important to adhere to the assigned visit schedule; and
 - The site shall attempt to ascertain whether or not the patient wishes to and/or should continue in the study; and
- Prior to a patient being deemed lost-to-follow-up, the Investigator or designee must make every effort to regain contact with the patient. All attempts to regain contact with the patient must be recorded in the patient's medical record. If the patient continues to be unreachable, the patient will be considered to have withdrawn from the study.

4.7. Study Completion

Primary study completion is defined as the completion of the Week 12 visit, even if 1 or more interim visits or procedures was/were missed.

Completion of the Safety Follow-Up Period is defined by the completion of the Week 20 visit, even if 1 of the 2 visits is missed or if procedures were missed.

5. STUDY TREATMENTS

5.1. Treatment Groups

Patients will be randomized in a 1:1:1 ratio to 1 of the following dose cohorts:

- Dose Cohort 1: Ziltivekimab 15 mg
- Dose Cohort 2: Ziltivekimab 30 mg
- Dose Cohort 3: Placebo

5.2. Rationale for Dosing

The doses used in this study will include the dose used in the Cardiovascular Outcomes trial. In accordance with the planned primary analysis. The 15 mg and 30 mg dose used in the ongoing RESCUE study (COR-001-02) is planned for inclusion in this Japanese study.

5.3. Randomization and Blinding

This is a randomized, double-blind, placebo-controlled study. Treatments will be assigned to randomized patients via an interactive web-response system (IWRS). Patients will be randomized in a 1:1:1 ratio to receive Ziltivekimab 15 mg, Ziltivekimab 30 mg, or matching placebo. Patient randomization will be stratified by CKD stage which is stratified into two categories: (1) Stage 3 and (2) Stages 4 and 5.

This study is double-blind. The patients, Investigators, site personnel, site monitors, Sponsor, and contract research organization (CRO) clinical operational personnel will be blinded to the treatment assignment. Ziltivekimab and matching placebo will be provided as a liquid for SC injection.

The randomization list will be generated by an independent CRO statistician not otherwise involved in the study.

5.4. Breaking the Blind

In case of a medical emergency or medical situation in which the treatment assignment is necessary for proper patient management, the Investigator may obtain the treatment assignment from the IWRS. The Investigator should make every reasonable attempt to contact the Medical Monitor before unblinding a patient. In all cases, the Investigator must submit a written report, including all pertinent details, to the Medical Monitor within 24 hours of the unblinding.

5.5. Drug Supplies

5.5.1. Formulation and Packaging

The composition of Ziltivekimab for injection is displayed in Table 1.

Table 1 Composition of Ziltivekimab for Injection

Component	Amount per mL (15 mg Vial)	Amount per mL (30 mg Vial)	Amount per mL (Placebo Vial)
Ziltivekimab	15 mg	30 mg	0 mg
Trehalose dihydrate	50.00 mg	50.00 mg	50.00 mg
L-arginine monohydrochloride	14.75 mg	14.75 mg	14.75 mg
L-methionine	1.49 mg	1.49 mg	1.49 mg
L-histidine	1.55 mg	1.55 mg	1.55 mg
L-histidine monohydrochloride monohydrate	2.10 mg	2.10 mg	2.10 mg
Polysorbate 80	0.70 mg	0.70 mg	0.70 mg
Water for injection	qs to 1.0 mL	qs to 1.0 mL	qs to 1.0 mL
qs = quantum satis.			

5.5.2. Study Drug Preparation and Dispensing

The dose of Ziltivekimab for SC injection must be prepared using aseptic techniques. Drug product is presented as a single use vial.

Ziltivekimab is supplied as a liquid for injection.

Personnel responsible for study drug preparation should have an appropriate background (ie, physician, pharmacist, pharmacy technician, nurse, or other personnel approved by the Sponsor) and be appropriately trained. Please see Pharmacy Manual for full details. The final required volume of Ziltivekimab is provided in Table 2.

Please see the Pharmacy Manual for instructions on preparing and administering the study drug and storage of prepared study drug.

Table 2 Planned Study Drug Doses and Administered Volumes

	Dose Cohort 1	Dose Cohort 2	Dose Cohort 3
Study drug name	Ziltivekimab	Ziltivekimab	Placebo
Type	Active drug	Active drug	Comparator
Dose	15 mg	30 mg	Not applicable
Dose administration	15 mg in 1 mL injection	30 mg in 1 mL injection	1 mL placebo injection
Route of administration	SC injection	SC injection	SC injection
SC = subcutaneous.			

5.5.3. Study Drug Administration

One mL of the assigned study drug will be administered SC by trained study site personnel. The date and time of study drug administration must be recorded in the appropriate sections of the electronic case report forms (eCRFs).

5.5.4. Treatment Compliance

To ensure treatment compliance, study drug will be administered under the supervision of site personnel. The date, time, and volume (dose) of study drug administered will be recorded in the appropriate sections of the eCRFs.

5.5.5. Storage and Accountability

Ziltivekimab and placebo must be stored at 2 to 8°C in the original container and must not be frozen.

The dispensing pharmacist or designated qualified individual will write the date dispensed, dose dispensed, and the patient's identification number on the Drug Accountability Source Documents. All medication supplied will be accounted for on the Drug Accountability Record. All partially used or unused drug supplies will be destroyed at the site in accordance with approved written site procedures or returned to Corvidia. The Investigator will maintain a record of the amount and dates when unused supplies were either destroyed or returned to Corvidia. All records will be retained as noted in Section 11.6.

5.6. Management of Specific Adverse Events

5.6.1. Injection-Related Reactions, Hypersensitivity, and Anaphylaxis

Patients will be carefully monitored for 1 to 2 hours at the site post every dosing. If any safety concerns are observed between the first and second doses, the Investigator/Sponsor will investigate the discontinuation of further doses and/or the entire study.

Signs of a possible injection-related reaction include fever, chills, pruritus, and urticaria.

Anaphylaxis is a severe, potentially fatal, systemic allergic reaction that occurs suddenly after contact with an allergy-causing substance, such as an investigational product.

For the purposes of this study, a hypersensitivity reaction is defined as an acute onset of an illness with involvement of the skin, mucosal tissue, or both during injection of the study drug (but does not meet the definition of anaphylaxis described above).

If signs and symptoms of injection-related reactions are observed and the patient's cardiovascular status is stable, treat the patient as follows:

- If the patient continues to show signs and symptoms of hypersensitivity, administer an SC dose of antihistamine, if the Investigator believes this is appropriate.
- In patients who have experienced mild or moderate injection reactions in the past or there is concern that the patient may develop an injection reaction, antihistamines and/or acetaminophen may be administered prophylactically prior to subsequent injections, at the discretion of the Investigator.
- In patients who experience severe (Common Terminology Criteria for Adverse Events [CTCAE] Grade ≥ 3) injection-related reactions, anaphylaxis, or hypersensitivity, treat the patient as follows:
 - Permanently discontinue the study drug;
 - Treat the patients as for an anaphylactic reaction with IV antihistamines, corticosteroids, epinephrine, inhaled bronchodilators, and other measures as necessary; and
 - Obtain a blood sample to determine the presence of anti-drug antibodies (ADAs).

Note: The patient should remain in the study for the End of Treatment Visit and safety follow-up.

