1.4.2. Phase 1 Study in Patients With Chronic Kidney Disease (COR-001-SC1)

[figure not shown]
This study was a Phase 1, randomized, double-blind, placebo-controlled, cohort dose-escalation study in patients with CKD to assess the safety, PK, and pharmacodynamics (PD) of a single dose of Ziltivekimab. The study population had moderate-to-severe CKD (ie, eGFR 20 to 60 mL/min/1.73 m²) who had serum CRP levels >2 mg/L over 2 consecutive measurements. The primary objective evaluated the safety of single SC doses of Ziltivekimab (planned doses of 5, 15, 50, and 100 mg). The main secondary objective evaluated single-dose PK of SC Ziltivekimab and the effects of Ziltivekimab on CRP and serum amyloid A (SAA).

After SC administration, Ziltivekimab concentrations reached peak levels by 7 to 17 days after dosing, on average, and serum Ziltivekimab concentrations remained quantifiable up to 217 days

postdose in all patients. Ziltivekimab concentrations increased in a dose-dependent manner. Terminal slopes (half-life) appeared similar for the 5 and 15 mg doses, suggesting linear PK. High intersubject variability among the 3 patients in the highest dose cohort (50 mg) confounded the interpretation for that dose. One patient in the 50 mg dose cohort had levels 2- to 3-fold higher than the other 2 patients so that it appeared that the latter patients displayed a less than dose proportional increase, while the former showed a greater than dose proportional increase in Ziltivekimab serum levels.

Mean hs-CRP levels were comparable and elevated at Baseline across placebo and the Ziltivekimab treatment groups, suggesting systemic inflammation. Figure 2 presents the percentage of patients who achieved an hs-CRP level of <2.0 mg/L from Baseline to Week 32. A consistent decrease in hs-CRP levels was observed in the Ziltivekimab dose groups throughout the first 8 weeks post randomization, while levels in the placebo group increased over time.

Figure 1 Percentage of Chronic Kidney Disease Patients Treated With Ziltivekimab or Placebo Who Achieved a High-Sensitivity C-Reactive Protein Level of <2.0 mg/L From Baseline to Week 32

hs-CRP = high-sensitivity C-reactive protein.

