6.3.1. Visit 1 (Day 1)

The following procedures will be performed at Visit 1 (Day 1):

- Reaffirm inclusion/exclusion criteria;
- Update medical history;
- Record prior/concomitant medications;
- Obtain vital signs;
- Collect sample for chemistry and hematology assessments;
- Collect sample for urinalysis (including albumin);
- Collect sample for lipids and subfractions assessment;
- Collect sample for IL-6 (total) assessment (predose);
- Collect sample for hs-CRP assessment;
- Obtain BMI;
- Collect Ziltivekimab PK sample;
- Randomize patient;
- Collect ADA sample;
- Collect sample for fibrinogen, SAA, NT-pro-BNP, hemoglobin and albumin assessments;
- Collect sample for INR assessment (only for patients currently receiving warfarin);
- Assess AEs; and
- Administer assigned study drug (after all other Day 1 assessments).

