6.3.3. Visit 3 (Week 2, Day 15 + 3 days)

The following procedures will be performed:

- Record prior/concomitant medications;
- Obtain vital signs;
- Collect sample for chemistry and hematology assessments;
- Collect sample for IL-6 (total) assessment;
- Collect sample for hs-CRP assessment;
- Collect Ziltivekimab PK;
- Collect ADA sample;
- Collect sample for INR assessment (only for patients currently receiving warfarin); and
- Assess AEs.

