6.3.5. Visit 5 (Week 4, Day 29 + 3 days)

- The following procedures will be performed: Record prior/concomitant medications;
- Obtain vital signs prior to electrocardiogram (ECG) recording;

- Perform 12-lead ECG;
- Collect sample for chemistry and hematology assessments;
- Collect sample for IL-6 (total) assessment (predose);
- Collect sample for hs-CRP assessment;
- Collect Ziltivekimab PK sample;
- Collect ADA sample;
- Collect sample for INR assessment (only for patients currently receiving warfarin);
- Assess AEs; and
- Administer assigned study drug (after all other Visit 5 assessments).

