6.3.7. Visit 7 (Week 8, Day 57 + 6 days)

The following procedures will be performed:

- Record prior/concomitant medications;
- Obtain vital signs prior to electrocardiogram (ECG) recording;
- Perform 12-lead ECG;
- Collect sample for chemistry and hematology assessments;
- Collect sample for IL-6 (total) assessment (predose);
- Collect Ziltivekimab PK sample;
- Collect ADA sample;
- Collect sample for INR assessment (only for patients currently receiving warfarin);
- Assess AEs; and
- Administer assigned study drug (after all other Visit 7 assessments).

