APPENDIX A: SCHEDULE OF PROCEDURES

	Screening: Days -14 Through -1 ^a	Treatment Period: Baseline Through Week 12									Safety Follow-Up: Weeks 12 Through 20	
Visit	-1	1	2 ^p	3	4 ^p	5	6 ^p	7	8	9/ET1	10	11/ET2
Week	-2		1	2	3	4	6	8	10	12/ET1	16	20/ET2
Day	-14 to -4	1	8+3 days	15+3 days	22+3 days	29+3 days	43+6 days	57+6 days	71+6 days	85+6 days	113+6 days	141+6 days
Informed consent ^b	X											
Inclusion/exclusion criteria	X	X ^c										
Demographic information	X											
Medical history/update	X	X										
Prior/concomitant medications	X	X	X	X	X	X	X	X	X	X	X	X
Limited physical examination ^d	X											X
Vital signs ^e	X	X		X	X	X		X		X	X	X
Infectious disease screen ^f	X ^g											
Serum pregnancy test ^h	X											X
FSH for postmenopausal women	X											
12-lead ECG ⁱ	X					X		X		X		X
Chemistry and hematology ⁿ	X ^g	X	X	X	X	X	X	X	X	X	X	X
Urinalysis (including albumin) ^j	X	X								X		
Lipids and subfractions (fasting 8 hours) ^{k,n}	X	X								X	X	
Spot urine protein-creatinine ratio ⁿ	X									X		
Screening IL-6 (central)	X											
IL-6 (Total) ⁿ		X ^l	X	X	X	X	X	X	X	X	X	X
hs-CRP ^{m,n}	X	X	X	X		X			X	X	X	X
BMI		X										
Ziltivekimab PK ⁿ	X	X	X	X	X	X	X	X		X	X	X

	Screening: Days -14 Through -1 ^a	Treatment Period: Baseline Through Week 12									Safety Follow-Up: Weeks 12 Through 20	
Visit	-1	1	2 ^p	3	4 ^p	5	6 ^p	7	8	9/ET1	10	11/ET2
Week	-2		1	2	3	4	6	8	10	12/ET1	16	20/ET2
Day	-14 to -4	1	8+3 days	15+3 days	22+3 days	29+3 days	43+6 days	57+6 days	71+6 days	85+6 days	113+6 days	141+6 days
Randomization		X										
Study drug administration (post-assessments)		X				X		X				
ADA ⁿ	X	X	X	X	X	X	X	X	X	X	X	X
Fibrinogen, serum amyloid A, NT-pro-BNP, hemoglobin and albumin ⁿ		X							X	X		
INR ^o		X	X	X	X	X	X	X	X	X		
Adverse events	X	X	X	X	X	X	X	X	X	X	X	X

ADA = anti-drug antibody; BMI = body mass index; ECG = electrocardiogram; ET1 = Early Termination for Treatment Period, ET2 = Early Termination for Safety Follow-up Period; FSH = follicle-stimulating hormone; HIV = human immunodeficiency virus; hs-CRP = high-sensitivity C-reactive protein; IL = interleukin; INR = international normalized ratio; lab = laboratory; PI = Principal Investigator; PK = pharmacokinetic(s).

^a Screening may be extended up to 1 week to allow for retesting of a hs-CRP result that did not meet inclusion criteria.

^b Signed informed consent must be obtained before any study-related procedures are performed.

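### No vital signs are scheduled in the 1–2 hours after any injection, so the scheduled vital-sign tables carry no information on acute post-injection effects

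*Protocol*

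**What the plan says.** Protocol 5.6.1 sets an on-site observation period: "Patients will be carefully monitored for 1 to 2 hours at the site post every dosing". The same section names fever among the signs of an injection-related reaction and makes management depend on whether the patient's cardiovascular status is stable. Protocol 8.13 defines vital signs as temperature, respiratory rate, heart rate and blood pressure.

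The visit lists put dosing last each time:

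- Visit 1 (6.3.1): "Administer assigned study drug (after all other Day 1 assessments"
- Visit 5 (6.3.5): "Administer assigned study drug (after all other Visit 5 assessments"
- Visit 7 (6.3.7): "Administer assigned study drug (after all other Visit 7 assessments"

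Appendix A labels its dosing row "Study drug administration (post-assessments". Section 6 and Appendix A agree that vital signs are taken at Visits -1, 1, 3, 4, 5, 7, 9, 10 and 11, and not at Visits 2, 6 or 8.

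Vital signs are a named safety endpoint (Protocol 8.11, SAP 2.3.4). SAP 3.6.3 summarizes them by visit and by threshold, with no post-dose timepoint.

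**The concern.** Patients are kept on site after each injection so that reactions can be seen, and the quantities most likely to move in such a reaction are the four vital signs. The schedule collects them only before the injection, and the next set is two to nearly five weeks away. A vital-sign table with no difference between arms could then be misread as evidence of no acute hemodynamic or febrile response to the injection, when no scheduled reading was taken at a time that could show one.

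Safety is the trial's secondary objective, and 5.6.1 has safety concerns between the first and second doses prompt a review of further dosing. Comparable by-arm readings from the observation period would support both.

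**Working it through.** **Inputs.** Visit windows from Protocol 6.3 and Appendix A: Visit 1 Day 1; Visit 3 Days 15–18; Visit 4 Days 22–25; Visit 5 Days 29–32; Visit 7 Days 57–63; Visit 9 Days 85–91. Doses are given at Visits 1, 5 and 7.

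**The plan's own figure.** SAP 2.2.3 gives a 28-day dosing interval. Nominal days reproduce it: 29 − 1 = 28 and 57 − 29 = 28.

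**Days from each dose to the next scheduled vital signs.** Minimum = earliest day of the next vital-sign visit − latest day of the dosing visit. Maximum = latest day of the next vital-sign visit − earliest day of the dosing visit.

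| Dose | Next vital signs | Nominal | Minimum | Maximum |
|---|---|---|---|---|
| 1 (Visit 1) | Visit 3 | 15 − 1 = 14 | 15 − 1 = 14 | 18 − 1 = 17 |
| 2 (Visit 5) | Visit 7, predose | 57 − 29 = 28 | 57 − 32 = 25 | 63 − 29 = 34 |
| 3 (Visit 7) | Visit 9 | 85 − 57 = 28 | 85 − 63 = 22 | 91 − 57 = 34 |

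Vital-sign sets scheduled within the observation period: 0 of 3 doses. No scheduled reading falls earlier than 14 days after any dose.

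**Coverage near peak.** Protocol 1.4.2 reports: "Ziltivekimab concentrations reached peak levels by 7 to 17 days after dosing". Visit 3, at 14–17 days after dose 1, lies inside that range. Visit 4, at 21–24 days (22 − 1 to 25 − 1), adds a second mid-interval reading unless it is converted to a phone visit. After doses 2 and 3 the first reading (22 days at the earliest) falls beyond the range.

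**What happens if a site records a post-dose value anyway.** Under SAP 3.1.2 a scheduled reading takes precedence over an unscheduled one in the same analysis window. At Visits 5 and 7 the predose reading would therefore displace the post-dose one in the by-visit summary. On Day 1 the post-dose value falls in the Baseline window, which runs through Day 1, although SAP 3.1.3 defines baseline as predose. It has no slot of its own.

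**Thresholds.** Protocol 9.2.3.3 lists SBP change >25%, SBP >160 or <90, HR >100 or <50, and respiration rate >24. SAP Table 1 in 3.6.3 keeps the SBP change, SBP >160, HR >100 and respiration rate >24 but omits SBP <90 and HR <50. SAP section 5 records no changes from the protocol's analyses. Adding post-dose readings to SAP Table 1 as it stands would still leave an absolute low pressure or low heart rate uncounted.

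**The case against.** The strongest reply is that injection reactions are captured elsewhere, and that is correct. Protocol 8.7 requires hypersensitivity and anaphylaxis to be reported within 24 hours. Protocol 8.3 makes Grade ≥3 injection-related reactions and anaphylaxis AESIs, with a dedicated eCRF for anaphylaxis. SAP 3.6.1 compares these by arm and tabulates TEAEs by occurrence time. Staff observing a patient may well take vital signs, and an unscheduled outlier could enter the SAP 3.6.3 threshold count, which asks for at least one post-baseline outlier value. What remains is that such readings would be taken selectively and not for every patient at a common time, and that they have no place in the by-visit summary.

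A reader might infer more than the documents support:

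- **That the vital-sign endpoint cannot show any early effect, or that every reading is predose or end-of-interval.** Visit 3, and Visit 4 if on site, contradict this for dose 1. The statement is also limited to scheduled data.
- **That the stopping rule is impaired.** Protocol 4.3 is triggered by anaphylactic events in at least 10% of patients. It uses no vital-sign reading and does not count other injection reactions.
- **That Visit 8 needs an ECG because none is scheduled near peak.** The half-life makes this a weak argument. Assume exponential decay from a peak at 7–17 days and the 38–44 day half-life in Protocol 1.4.3 (from IV dosing in hemodialysis patients, so only a guide). The level 28 days after a single dose is then 2^(−21/38) = 0.68 to 2^(−11/44) = 0.84 of its peak. Adding what remains of dose 1, the predose level at Visit 7 is 0.68 + 0.41 = 1.09 to 0.84 + 0.54 = 1.38 times the first-dose peak, where 0.41 = 2^(−49/38) and 0.54 = 2^(−39/44). A sustained concentration-related effect would be visible at existing visits, and an ECG two weeks after dosing would not catch a brief injection effect.

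**Conclusion.** The point holds for acute post-injection effects on vital signs: 0 of 3 doses have a scheduled reading in the observation period, and the next comes 14–17, 25–34 and 22–34 days later. It rests on patients following the visit windows, without early termination or an unscheduled visit, and on reading the procedure lists and Appendix A as the full set of planned measurements.

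The documents do not contradict each other on the schedule, so this is a design improvement of low severity. The mismatch between SAP Table 1 and Protocol 9.2.3.3 is a genuine inconsistency and needs reconciling in any case.

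**What to change.** 1. In Protocol Appendix A and sections 6.3.1, 6.3.5 and 6.3.7, record one vital-sign set during the existing observation period at Visits 1, 5 and 7, with its clock time.
2. In SAP 3.1.2, define this as a separate post-dose timepoint, so that the Day 1 reading does not fall in the Baseline window and the predose readings at Visits 5 and 7 do not displace the others.
3. In SAP 3.6.3, summarize the post-dose timepoint by arm and include it in the threshold counts.
4. Reconcile SAP Table 1 with Protocol 9.2.3.3 on SBP <90 and HR <50, so that low values are counted, or list the difference in SAP section 5.

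The cost is a few minutes at visits where the patient is already under observation, at most 36 × 3 = 108 extra vital-sign sets, and one more timepoint in the tables. No visit or staff is added, and no dose or management rule changes. If the sponsor prefers not to add the measurement, the protocol should at least say whether readings taken during the observation are recorded, and the SAP how they are analyzed.

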5.7. Prior and Concomitant Medications and/or Procedures

5.7.1. Excluded and Restricted Medications and/or Procedures

See Section 4.1 and Section 4.2 for restrictions on prior medications and treatments.

Patients with cardiovascular disease should be treated according to published guidelines throughout the study; in addition, patients may receive concomitant medications as clinically indicated with the following restrictions:

- Patients using herbal remedies and supplements must be on a stable dose and brand of product and new treatments may not be started during the study.
- Systemic immunosuppressive drugs (such as cyclosporine, tacrolimus, sirolimus, mycophenolate, and oral and IV glucocorticoids other than prednisone [or equivalent] up to a dose of 5 mg per day) may not be prescribed at any time during the study. Topical use (eg, cyclosporine eye drops) is not restricted.

Note: Use of otic, ophthalmic, inhaled, and topical corticosteroids or local corticosteroid injections are not restricted. Short-term systemic glucocorticoid use (ie, <5 consecutive days) for managing acute illnesses is also not restricted.

- Narrow therapeutic window medications that are influenced by cytochrome P450 enzymatic pathways may not be prescribed at any time during study. Such medications include the following:
 - Digoxin;
 - Theophylline;
 - Terfenadine;
 - Tizanidine;
 - Quinidine;
 - Phenytoin and its derivatives (eg, fosphenytoin, mephenytoin, dantrolene, enzalutamide, allantoin, ethoin, neocitrullamon);
 - Taxane chemotherapeutic agents;
 - Cyclosporine;
 - Mammalian target of rapamycin inhibitors (eg, sirolimus, tacrolimus);
 - Ergot alkaloids;
 - Antipsychotic medications (specifically pimozide, thioridazine); and
 - Fentanyl and derivatives (eg, alfentanil and sufentanil).
- Live/live attenuated vaccine product
- Other investigational drugs
- Warfarin is permitted, but the international normalized ratio (INR) must be monitored closely and, at minimum, according to the protocol Schedule of Procedures (see Appendix A).
- Blood transfusion
- Coronary revascularization (percutaneous coronary intervention or coronary artery bypass grafting) or any other major surgical procedure
- Organ transplant
- Indwelling catheter

